#### Phototoxicity

BVD-523 exhibits an absorbance peak in the range of UV-A/UV-B light, specifically at ~320 nm. Clinical studies of other drugs that modulate MAPK pathway components have exhibited skin phototoxicity.

Beyond dermatological monitoring (above), potential risks of direct phototoxicities induced by BVD-523 will be reduced by advising that patients minimize sun exposure, use broad-spectrum sunscreens, and wear sunglasses. Patients will be informed that relevant sun exposure may occur even through glass, such as while driving.

### **Ophthalmological Effects**

Preclinical toxicology studies of BVD-523 have not revealed any exposure-dependent ophthalmological toxicities; however, clinical studies of MEK1/2 kinase inhibitors highlight ocular toxicities that may reflect mechanistically attributable risks observable in a proportion of patients. Of particular concern are the following dose-limiting toxicities comprising exposuredependent, serious adverse events during clinical studies: retinal vein occlusion, retinal detachment and related vision abnormalities. In the ongoing first-in-man Phase 1 study, thru 1-April-2014, a single AE of vision changes has been reported in a single patient on a low dose of BVD-523 (20 mg, b.i.d.). While it is not definitively understood whether ocular toxicities reflect primary pharmacology associated with global inhibition of the MAPK pathway, specific management and exclusion criteria are defined in this clinical protocol, as the toxicities could potentially severely and irreversibly impact patient well-being.

### **Gastrointestinal Toxicity**

Preclinical toxicity studies of BVD-523 have provided evidence of exposure-related, reversible gastrointestinal toxicities, and these toxicities have also been observed at high frequency in the first 18 patients in the ongoing first-in-man Phase 1 study of advanced malignancies (Protocol BVD-523-01), in once case leading to an SAE of renal insufficiency secondary to dehydration. The severity and reversibility of these non-clinical and clinical toxicities, while not meriting a specific monitoring or treatment plan, warrant active routine monitoring of patients for this toxicity.

### **QTc Prolongation**

The balance of preclinical evidence suggests BVD-523 has low, but observable, potential to cause QT prolongation. Due to potentially unique species sensitivity, as well as possibly unknown consequences following chronic dosing, patients dosed with BVD-523 in the first-in-human study, BVD-523-01, are being monitored for potential QTc prolongation and related cardiotoxicities via Holter monitoring. No clinically significant cardiac abnormalities have been seen to date in the first trial (BVD-523-01). QTc assessment will be performed at baseline and on Day 8, at steady state.

#### **Tissue Mineralization**

Tissue mineralization has been observed in rodent toxicology studies of BVD-523. The incidence and severity of mineralization was dose-dependent and effects were observed in one or more tissues at toxic doses. In animals in which mineralization occurred after treatment with BVD-523, significantly increased serum phosphorus and modestly decreased serum calcium were seen. These effects were not observed in animals in which there was no mineralization.

Tissue mineralization has been reported in rodents with other compounds that target the MAPK pathway and published studies suggest that the MAPK pathway is a negative regulator of matrix mineralization both *in vitro* and *in vivo*.

Routine clinical laboratory tests, including blood chemistry analyses for calcium and inorganic phosphate, will be performed and any indication of abnormalities may result in further investigations. A clinical monitoring strategy similar to this was previously employed for related drugs that target the MAPK pathway.

#### Hematological Effects

Hematological effects observed in a rat repeat dose study included lowered reticulocyte counts, mean corpuscular volume, platelet counts (in females only) and increased neutrophil, monocyte, basophil and large unstained cell counts. In dogs the clinical pathology findings were consistent with inflammation (increased white blood cell count, neutrophils, fibrinogen and globulin) and decreased albumin and hemorrhage (decreased red cell mass).

In order to monitor for potential hematologic toxicity in humans, routine clinical laboratory hematology tests, should be performed and any indication of abnormalities may result in further investigations.

## 1.5.2 Pharmacology Studies

BVD-523 is highly efficacious *in vivo* when administered as a single agent in ectopic xenograft models of colon, pancreatic and melanoma cancers, 3 tumor types in which ERK is known to be highly activated. Notably, partial regression was achieved in a colon cancer model (Colo205) when the compound was administered at 50 mg/kg (b.i.d.). Biomarker analyses confirmed that improved efficacy obtained at higher doses of BVD-523 correlated with increasing ERK inhibition.

### 1.5.3 Toxicity and Safety Studies

When BVD-523 was characterized using *in vitro* screens against 66 receptors and ion channels, no toxicologically significant interactions were identified. Additionally, BVD-523 was negative in bacterial mutation and *in vivo* micronucleus screening assays; therefore, BVD-523 is not considered to have a significant genetic toxicology risk.

While BVD-523 modestly inhibits the human ether-a-go-go related gene (hERG) current (IC50 3.4  $\mu$ M), no significant effects were seen in action potentials recorded from dog Purkinje fibers exposed to up to 10  $\mu$ g/mL and no significant cardiovascular findings were observed upon acute oral dosing of the compound at dose levels up to 50 mg/kg in dogs (Cmax = 17.3  $\mu$ M). Thus BVD-523 is considered to have a low potential to cause QT prolongation in patients, but, as stated, the first-in-human study will monitor for signs of cardiovascular effects of BVD-523 in humans.

No significant cytochrome P450 (CYP) inhibition has been observed with the compound.

*In vitro* studies suggest that the compound is metabolized primarily via oxidation by multiple CYPs including 3A4, 2D6, and 1A2. Furthermore, no significant CYP induction was observed after up to 14 days drug treatment in rats, nor during *in vitro* studies with human hepatocytes. These data suggest a limited potential for drug-drug interactions.

BVD-523 HCl salt is orally available in multiple species (absolute bioavailability %F = 23% in dog to 100 % in monkey) when formulated as a simple suspension in 1% carboxymethyl-cellulose (CMC) and has a half-life of 2-4 hours across all species.

BVD-523 was administered to male and female Sprague-Dawley rats in several toxicology studies: (1) a GLP study for up to 28 days at dose levels up to 50 mg/kg/day twice daily; (2) for up to 14 days at dose levels up to 100 mg/kg twice daily; and (3) for up to 5 days at dose levels up to 150 mg/kg/dose once daily. The incidence and severity of mineralization seen in these studies was dose-dependent and effects were observed in one or more tissues at toxic doses. In animals in which mineralization occurred after treatment with BVD-523, significantly increased serum phosphorus and modestly decreased serum calcium were seen. These effects were not observed in animals in which there was no mineralization. Therefore, the risk of tissue mineralization can be assessed by serum phosphorus and calcium monitoring. A clinical monitoring strategy similar to this was previously employed for related drugs that target the MAPK pathway because those compounds likewise elicited mineralization in rodents.

When BVD-523 was administered to male and female Sprague-Dawley rats for up to 28 days at a dose level of 25 or 50 mg/kg twice daily, BVD-523 was poorly tolerated. Although most clinical signs and clinical pathology findings reversed following 4 weeks of recovery, skin lesions and histopathology findings persisted in many tissues at both dose levels after the recovery. Based on these findings, 25 and 50 mg/kg twice daily dose levels were considered severely toxic. Administration of 12.5 mg/kg twice daily for 28 days was generally well-tolerated by rats of both sexes; however, this dose level was associated with test article-related findings that included (1) swelling in the neck, (2) decreased forelimb strength, (3) multiple clinical pathology findings, and (4) enlarged lymph nodes, spleen, and mammary gland. Based on these observations, the severely toxic dose in 10% of the animals (STD10) for BVD-523

when administered for up to 28 days in Sprague-Dawley rats is 12.5 mg/kg given twice daily (25 mg/kg/day). On Day 28 of the dosing phase, this dose level corresponded with a  $C_{max}$  of 28700 and 15323 ng/mL and AUC0-12 of 264868 and 124341 hr.ng/mL for males and females, respectively.

BVD-523 was administered to male and female beagle dogs for up to 28 days at dose levels of 15, 5, or 2 mg/kg twice daily. Initial analysis of the toxicity profile observed shows that BVD-523 was well tolerated in dogs. The rat was designated the most sensitive species and rat data were used to calculate the starting dose in man.

Based on the data accumulated to date, BVD-523 possesses a toxicology profile which presents no impediment to its development as an anti-cancer agent.

For further information, please refer to the BVD-523 Investigator's Brochure (Version 2.0, 21 April 2014).

# 2 RATIONALE FOR THE STUDY

The overall purpose of this study is to support the development of an oral formulation of BVD-523 for the treatment of patients with AML or MDS. BVD-523 is a highly potent, selective, and pharmacologically active inhibitor of ERK family kinases. The compound has demonstrated efficacy as a single agent in preclinical models of colon, pancreatic and melanoma cancers (Section 1.5.2), and has potential for application alone or in combination with existing cancer chemotherapeutics.

This study is being performed to assess the safety, tolerability, and preliminary clinical effects of BVD-523 given orally, twice daily for 21-day cycles, in patients with AML or MDS. The pharmacokinetics and pharmacodynamics of BVD-523 will also be explored after the first doses administered on Day 1 and at steady state on Day 22. Subsequent assessments may be done as indicated after completion of Cycle 1.

# 2.1 RATIONALE FOR THE DOSES AND THE DOSING REGIMEN

The human Phase 1 starting dose for BVD-523 in the first trial (BVD-523-01) was derived from 28-day GLP toxicology studies performed in rodent and non-rodent species and calculated as described by Senderowicz (83). Specifically, our results indicated that toxicity in rodents would be used to establish starting dose in patients. The severely toxic dose in 10% of the animals (STD10) for BVD-523 when administered for up to 28 days in Sprague-Dawley rats was determined to be 12.5 mg/kg dosed twice daily (25 mg/kg/day). A standard 10-fold reduction of this dose was scaled to establish a starting dose of 13.5 mg twice-daily of BVD-523 (free base equivalents) or 14.6 mg twice-daily of BVD-523, based on an average body surface area of 1.8 m^2 consistent with current clinical practice and dosing convenience, the proposed starting dose for the first Phase 1 clinical study with BVD-523 in cancer patients (BVD-523-01) was 10 mg twice-daily (20 mg/day) (84).

The starting dose determination for this Phase 1/2 study (BVD-523-02) in AML or MDS patients described herein is based on the clinical experience during the dose-escalation study in patients with solid tumors. The dose escalation phase of study BVD-523-01, the first-in-man Phase 1 clinical study included 27 patients treated at dose levels of 10, 20, 40, 75, 150, 300, 600, 750, and 900 mg b.i.d. DLTs were observed in 5 pts: 2 with grade 3 rash (600 mg and 750 mg b.i.d.), 1 with grade 3 pruritus and elevated AST (900 mg b.i.d.), 1 with grade 3 diarrhea, vomiting, dehydration and elevated creatinine (900 mg b.i.d.), and 1 with grade 2 hypotension, elevated creatinine, and anemia (750 mg b.i.d.); the MTD was established at 600 mg b.i.d. BVD-523 achieved pharmacologically relevant exposure and manageable tolerability at its MTD of 600 mg b.i.d (82). Ex vivo whole blood assays demonstrated inhibition of phosphorylation of RSK, a downstream substrate of the target ERK, at doses  $\geq$  40 mg, b.i.d. Additionally, inhibition of metabolic activity was demonstrated by FDG-PET at 75 mg, b.i.d. The 300 mg b.i.d. starting dose for the BVD-523-02 study with AML or MDS patients is based upon these results in the solid tumor study. As the ongoing Phase 1 study progresses, the 300 mg b.i.d. starting dose in AML or MDS patients may be revised based upon accruing safety experience and determination of the RP2D from the solid tumor study.

# 3 STUDY DESIGN

### 3.1 STUDY DESIGN OVERVIEW

This is an open-label, multi-center Phase 1/2 study with a dose-escalation phase (Part 1) and a cohort expansion phase (Part 2) in patients with Acute Myelogenous Leukemia (AML) or Myelodysplastic Syndrome (MDS). This study will be conducted at up to 6 study centers.

#### 3.1.1 Study Objectives

#### 3.1.1.1 Primary Objectives

- To define the safety and tolerability of BVD-523 in patients with AML or MDS determining the dose-limiting toxicities (DLT), the maximum tolerated dose (MTD), and the recommended Phase 2 Dose (RP2D).
- To determine the pharmacokinetic profile of BVD-523 and selected metabolites in patients with AML or MDS.

#### 3.1.1.2 Secondary Objectives

- To assess clinical response in patients with AML or MDS treated with BVD-523 at the recommended Phase 2 dose (RP2D).
- To determine the progression-free survival (PFS) and duration of response (DOR) of AML or MDS patients treated with BVD-523 achieving CR/CRp.

#### 3.1.1.3 Exploratory Objective

• To evaluate pharmacodynamic marker (biomarker) measures.

### 3.1.2 Methodology / Study Design

BVD-523-02 is an open-label, multicenter, Phase 1/2 study with a dose-escalation phase (Part 1) and a cohort expansion phase (Part 2).

#### Part 1 Dose-escalation Phase:

A classic "3+3" design will be used to establish dose limiting toxicities (DLT), maximum tolerated dose (MTD), and the recommended Phase 2 dose (RP2D). Three to six patients per treatment cohort will be assigned to receive sequentially higher oral doses of BVD-523 on a twice daily schedule (b.i.d.) for 21 days (a "Cycle"), starting at a dose of 300 mg twice daily. Patients will receive twice-daily oral doses of BVD-523 until disease progression, unacceptable toxicity, or a clinical observation satisfying another withdrawal criterion is noted. Treatment cycles will occur consecutively without interruption, except when necessary to manage adverse events. All dose-escalation decisions will be based on Cycle 1 safety data and doses will not be escalated unless the patients receiving the highest current dose have been observed for at least 21 days (1 cycle).

The classic 3 + 3 design will be conducted as follows. Initially, 3 patients will be enrolled to a cohort; the occurrence of a single drug-related DLT in one of these 3 patients will prompt enrollment of up to 3 additional patients to that same cohort. When more than 1 DLT occurs in

 $\leq$  6 patients in a dosing cohort, dose escalation will be stopped and this dose level will be identified as the non-tolerated dose.

Doses between the non-tolerated dose and the preceding lower dose, where  $\leq 1$  DLT occurred, may be explored to more precisely define the MTD. This strategy allows for a rigorous determination of MTD, especially if the dose increase that resulted in determination of the non-tolerated dose is relatively large (i.e., > 50%).

During the study, the Safety Monitoring Committee may request that cohorts be enlarged or that evaluation of intermediate doses between 2 planned escalation steps be explored. Such requests will be discussed with the Investigator(s), Sponsor and Medical Monitor, and should be based on all data existing at that time, including safety and clinical activity, determinations of pharmacokinetics, pharmacodynamics, and cumulative toxicity. Before each escalation, investigators will be consulted to ensure that all involved agree with the escalation decision.

In addition, intra-patient dose escalation will be allowed after a patient has completed at least one cycle at their assigned dose, with escalation up to a dose where at least 3 patients have completed at least one cycle.

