#### Table 3.1Study Medication Dosing and Pharmacokinetics/Pharmacodynamics Chart

	Study Days			
	1	8± 1	15± 1	22± 1
BVD-523 dosing a	Х	Х	Х	Х
Pharmacokinetics	Х			Х
Pharmacodynamics	Х			Х

Dosing is twice daily in 21-day cycles until disease progression. Patients will take their study medication in the clinic on PK days. Patients may be treated beyond disease progression for additional 21-day cycles at the same or escalated dose level (see intra-patient dose escalation Sec 3.1.3) at the Investigator's discretion. Study medication for a week of dosing should be dispensed at each visit for treatment Cycles 1 and 2. For treatment cycles after Cycle 2, study medication will be dispensed to support the entire 3 week cycle.

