## 3.1.3 Summary of Dose Escalation

#### Table 3.2Summary of Dose Escalation

Observed Safety Outcomes	Action
1 DLT in 3 patients	Expand cohort up to 6 patients
1 DLT in 6 patients	Escalate by $\leq 50\%$ to next dose level
> 1 DLT in $\leq$ 6 patients	Stop dose escalation

*Note*: DLT is defined in detail in Section 3.1.4.2 below.

Each cohort can only begin when the previous cohort has completed treatment to at least the end of Cycle 1 without fulfilling a criterion which would prevent dose escalation. Intra-patient dose escalation will be permitted with consensus among the Principal Investigator, Medical Monitor, and Sponsor, to a dose not to exceed that for which 21 days of treatment has been deemed safe.

Although dose escalation decisions will be taken upon review of the data from Cycle 1, safety data will also be collected from all patients continuing treatment and these data will be reviewed periodically by the Safety Monitoring Committee. Any detected cumulative toxicity may require later dose reductions or other action as appropriate, including having an effect on the RP2D.

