### 3 STUDY DESIGN

### 3.1 OVERALL STUDY DESIGN

This study is an open label, Phase 1/2 clinical trial in subjects with AML or MDS. The trial has a dose-escalation phase (Part 1) and a cohort expansion phase (Part 2).

Part 1 – Dose-escalation Phase: The dose-escalation phase is a 3+3 design to determine the dose limiting toxicities (DLTs), maximum tolerated dose (MTD), and recommended Phase 2 dose (R2PD) of BVD-523 given twice-daily. The starting dose of BVD-523 will be 300 mg BID. Treatment will be administered in continuous, sequential 21 day Cycles until disease progression, unacceptable toxicity, or another withdrawal condition is met. Dose-escalation decisions will be based on Cycle 1 data. Within-subject dose escalations are allowed after completing one Cycle at the initial dose, pending complete Cycle 1 data for the dose to be escalated to. The MTD will be determined based on the highest dose associated with no more than 1 DLT in fewer than 6 subjects. Cohorts will be based on 3 subjects, but can be enlarged as deemed necessary by the Safety Monitoring Committee. Once a dose associated with more than 1 DLT in fewer than 6 subjects has been identified, intermediate doses may be examined to obtain a better estimate of the MTD.

Part 2 – Cohort-expansion Phase: Approximately 40 additional subjects will be recruited to one of two groups:

- Group 1: RAS mutant positive AML or MDS  $(n \le 20)$
- Group 2: RAS mutant negative AML or MDS  $(n \le 20)$

Subjects in both groups will receive treatment at the Recommended Phase 2 Dose (RP2D). Subjects will receive twice daily oral doses of BVD-523 in 21-day treatment cycles until disease progression, unacceptable toxicity, or another withdrawal criterion is met. Treatment cycles will occur consecutively without interruption except when necessary to manage adverse events.

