## **AE Summaries**

A subject who reported multiple AEs that map to a common PT or SOC is counted only once for that PT or SOC at the highest severity reported and at the greatest relationship to study drug. The number and percentage of subjects who experienced at least one AE as well as subjects who experienced at least one TEAE will be tabulated by SOC and PT with respect to dose level treatment group for each study part. The same tabulation will also be applied to any treatment emergent SAEs and any TEAEs leading to premature discontinuation from the study as well as to any DLTs.

Page 28

<sup>1 All toxicities will be considered related to BVD-523 if they cannot be definitively explained by underlying disease, intercurrent illness or concomitant medications.

The number and percentage of subjects who experience at least one TEAE will also be tabulated by SOC and PT within each dose level treatment group with respect to relationship to study drug (unrelated and at least possibly related [combining events classified as either possibly related or related]) and severity (Grade 1 to Grade 5 and ≥Grade 3). The tabulation by relationship

(unrelated and at least possibly related) will also be applied to any treatment emergent SAEs (TESAEs).

Subject listings will also be provided for all AEs, all SAEs, all AEs leading to early discontinuation from the study, all AEs leading to study drug interruptions and length of interruptions.

Bar graphs of AEs in CTCAE Term will be displayed in decreasing order of incidence from most common to least common. Each bar in the plot will represent an AE in CTCAE Term. Severity of AE (grades) will be embedded in each bar using the percentages of subjects in each AE grade. These plots will be provided for all AEs, TEAEs, treatment-emergent SAEs, and AEs leading to premature discontinuation from the study.

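### Intra-patient dose escalation has no single entry condition, ceiling or decision-maker, and the SAP does not say to which dose later adverse events belong

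*Protocol*

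**What the plan says.** Protocol 3.1.2, in its Part 1 text, lets a patient move up after one completed cycle at the assigned dose, "with escalation up to a dose where at least 3 patients have completed at least one cycle".

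Protocol 3.1.3, below Table 3.2, puts it differently: "Intra-patient dose escalation will be permitted with consensus among the Principal Investigator, Medical Monitor, and Sponsor", and only "to a dose not to exceed that for which 21 days of treatment has been deemed safe".

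The footnote to Protocol Table 3.1 adds: "Patients may be treated beyond disease progression for additional 21-day cycles at the same or escalated dose level". It points to 3.1.3 and ends by referring to the investigator's discretion. SAP Table 3.3 repeats the footnote without the pointer.

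SAP 3.1, in its Part 1 paragraph, says: "Within-subject dose escalations are allowed after completing one Cycle at the initial dose, pending complete Cycle 1 data for the dose to be escalated to".

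On reporting, SAP 10.2 has adverse events "tabulated by SOC and PT with respect to dose level treatment group for each study part", and SAP 5.2 breaks safety down by dose level in both parts. The response objective in Protocol 3.1.1.2 is tied to the RP2D.

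**The concern.** A rule for raising a patient's dose has to say when a patient qualifies, how high the dose may go, who agrees, and in which part of the study it applies. Here the answers depend on the paragraph read, and up to 6 centres will read them. The most permissive wording counts completers. Completing a cycle is not the same as the dose having been tolerated.

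There is also a reporting question. Once a patient has moved up, events in later cycles occur at a dose other than the starting one. Protocol 3.1.3 and 3.1.4.3 let cumulative toxicity over several cycles inform the RP2D, so the dose to which those events are credited bears on a primary objective.

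**Working it through.** **Passages side by side**

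| Place | Own cycle completed? | Condition at target dose | Who agrees | Part |
|---|---|---|---|---|
| Protocol 3.1.2 | yes | at least 3 patients with one completed cycle | not stated | Part 1 text |
| Protocol 3.1.3 | not stated | 21 days judged safe | Principal Investigator, Medical Monitor, Sponsor | not stated |
| Protocol Table 3.1 footnote | not stated; applies after progression | by pointer to 3.1.3 | investigator's discretion, with pointer to 3.1.3 | not stated |
| SAP Table 3.3 footnote | as above | none, pointer absent | investigator's discretion | not stated |
| SAP 3.1 | yes | Cycle 1 data complete | not stated | Part 1 text |

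Protocol 3.1.2 and SAP 3.1 both lack a safety condition and an approver, and neither refers to Protocol 3.1.3.

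**Can a non-tolerated level meet the 3.1.2 condition?** Inputs are cohorts of 3 to 6, and a level classed as non-tolerated on more than 1 DLT in at most 6 patients (Protocol 3.1.2).
- 2 DLTs in 6: 6 − 2 = 4 DLT-free patients; observed rate 2/6 = 33.3%, which is not below the 33% in the MTD definition (Protocol 3.1.4.1).
- 3 DLTs in 6: 6 − 3 = 3 DLT-free patients; observed rate 3/6 = 50%.

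If those patients finish the cycle, the count of 3 is met in both cases.

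**How often would a failing level look like this?** Let q be the true DLT rate (assumed, since the documents give none) and b(3,k) the binomial probability of k DLTs in 3. With 3 patients and then 3 more after a single DLT:
- P(non-tolerated) = b(3,2) + b(3,3) + b(3,1) × [b(3,1) + b(3,2) + b(3,3)]
- P(non-tolerated with at least 3 DLT-free) = b(3,1) × [b(3,1) + b(3,2)]

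At q = 0.30, b(3,1) = 0.441, b(3,2) = 0.189 and b(3,3) = 0.027. The first is 0.216 + 0.441 × 0.657 = 0.506, the second 0.441 × 0.630 = 0.278, and the ratio 0.55. The same ratio is 0.63 at q = 0.20, 0.45 at 0.40 and 0.34 at 0.50. If enrolment stops at the second DLT, a level failing at the fourth patient no longer qualifies. At q = 0.30 the ratio is then 0.441 × (0.7 × 0.3 + 0.7² × 0.3) / 0.506 = 0.157 / 0.506 = 0.31.

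**Part 2.** The plan's own figure reproduces: 1 − 0.9^20 = 0.878, the stated 88% per group. The footnote names no part, and Protocol 5.5 gives Part 2 the same procedures as Part 1. Protocol 3.1.4.3 lets the RP2D lie below the MTD. If it does, even the 3.1.3 ceiling leaves room above the RP2D; if the two are equal, it leaves none. The footnote route opens only after progression, so a response would have to follow progression at the RP2D and then a dose increase. As an illustration that overstates the effect, dropping 2 or 4 of 20 patients altogether gives 1 − 0.9^18 = 0.850 or 1 − 0.9^16 = 0.815.

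**Attribution of events.** SAP 10.2 and 5.2 do not say whether dose level means the assigned dose or the dose at onset. SAP 14.3.1 plans tables of delays, interruptions and reductions, but none of increases. The DLT window is the first 21 days, and under 3.1.2 an increase comes only after a completed cycle, so DLT counts and the MTD are largely insulated.

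**The case against.** The strongest reply is that 3.1.2 and 3.1.3 are neighbouring subsections and can both be obeyed: the first sets entry conditions, the second a ceiling and an approver. Sites must follow the whole protocol, so a level that stopped escalation is barred. Protocol 3.1.2 also bases dose-escalation decisions on Cycle 1 safety data, and Protocol 8 requires fewer than 2 of 6 patients with dose-limiting effects before escalating. Those two statements mainly concern cohorts but point the same way. The Table 3.1 footnote cites 3.1.3, and its mention of discretion may cover only continued treatment after progression. The SAP Introduction defers to the protocol on study conduct, so SAP wording authorises no dosing.

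Most of this stands. A reader might infer that the protocol permits treatment at a non-tolerated dose. The documents as a whole do not support that, because it requires reading 3.1.2 without 3.1.3. What remains is that 3.1.2 reads as a complete permission, carries no pointer to 3.1.3, and names no approver.

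A reader might also infer that Part 2 responses obtained above the RP2D will distort the RP2D response result. That is not shown either. The Part 2 descriptions place treatment at the RP2D, Protocol 5.5 concerns visits, and the only unrestricted text applies after progression. The protocol plans no formal efficacy analysis (10.3.6).

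**Conclusion.** The inconsistency is real and is in current text. Its weight rests on the conflict over ceiling and decision-maker. Under 3.1.2 read alone, a level stopped at an observed DLT rate of 33% to 50% in 6 patients can qualify as a target. Among levels that fail, about 34% to 63% would have at least 3 DLT-free patients for assumed true DLT rates of 50% down to 20%. Those shares assume that both groups of 3 are filled and that DLT-free patients finish the cycle; they fall if enrolment stops at the second DLT. They measure how easily the wording can be met, not how often anyone would be moved up.

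The attribution gap is a second, smaller point. Events in later cycles after an increase can be tabulated under the lower starting dose. It does not extend to the DLT and MTD counts in any important way. For Part 2 the plan is unclear rather than wrong, and the effect on the response count is probably small.

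SAP 5.2 already names an RP2D of 600 mg, so some Part 1 decisions may be past. The documents do not say whether any patient was moved up or whether a higher level was tested.

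**What to change.** Reconcile Protocol 3.1.2, 3.1.3 and the Table 3.1 footnote with SAP 3.1 and the SAP Table 3.3 footnote. One statement should give the entry condition, the ceiling (saying expressly how it treats levels already classed as non-tolerated), the decision-maker, and whether it applies in Part 2. The other places should refer to it. Which rule is clinically right is for the sponsor and investigators to settle.

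In the SAP, define dose level for adverse events and tabulate treatment-emergent events by dose at onset beside assigned dose. A patient who moves up then appears under more than one dose, so the denominator for each column should be stated as well. The dose history is already planned as Listing 16.2.5.3. In the response listings (16.2.6.1 and 16.2.6.2), flag any response first met after an increase above the RP2D.

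The cost is a protocol clarification, a few sentences in the SAP, one extra adverse event table and one flag. No new data are collected.
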